5.1.5 Management of Allergic/Hypersensitivity Reactions to Mapatumumab/Placebo

The administration of any recombinant protein has the potential to induce local or system immunologic reactions; subjects could experience, for example, acute allergic reactions. To date, 2 such SAEs have been reported which were considered related to mapatumumab (hypersensitivity and angioedema/facial edema). In the event of allergic/hypersensitivity reactions, investigators will institute treatment measures according to best medical and nursing practice. Guidelines for treatment are provided in [Appendix 8](#).

For a NCI-CTCAE Version 4.0 Grade 3 or Grade 4 hypersensitivity reaction, treatment with mapatumumab/placebo will be discontinued.

If mapatumumab/placebo is discontinued for Grade 3 or Grade 4 hypersensitivity reactions, the subject will continue to receive sorafenib, until radiologic progression or unacceptable toxicity.

5.2 Sorafenib

5.2.1 Packaging, Labeling, Preparation, and Storage

Sorafenib is supplied as tablets, each containing 274 mg sorafenib tosylate, equivalent to 200 mg of sorafenib.

The recommended daily dose of sorafenib is 400 mg (2 x 200 mg tablets) taken orally twice daily without food (at least 1 hour before or 2 hours after a meal).

Sorafenib will be stored at room temperature (15-30°C, 59-86°F) in a dry place.

For country-specific formulation and packaging information, please refer to the instructions provided in the sorafenib product labeling.

Supplier: Commercially available.

5.2.2 Anticipated Toxicities with Sorafenib

Toxicities anticipated with the use of sorafenib include the following:

- Cardiac: Cardiac ischemia and/or infarction, hypertension.
- Dermatologic: Hand-foot skin reaction, rash/desquamation.
- Hemorrhagic: Increased risk of bleeding.
- Gastrointestinal: Gastrointestinal perforation.
- Other: Wound-healing complications, fatigue, weight-loss, alopecia, pruritis, dry skin, diarrhea, anorexia, nausea, vomiting, constipation, liver dysfunction and abdominal pain.

Laboratory abnormalities observed in hepatocellular carcinoma patients treated with sorafenib include hypophosphatemia, lipase elevations, amylase elevations, hypoalbuminemia, international normalized ratio elevations, lymphopenia and thrombocytopenia.

Refer to the product labeling accompanying the product for information approved in your country.

5.2.3 Alteration of Sorafenib Dose/Schedule Due to Toxicity

Sorafenib may be reduced or delayed for toxicities considered related to sorafenib as described below, or if the investigator believes that a reduction in dose is warranted in the interest of subject safety. When a dose reduction is necessary, sorafenib dose may be reduced to 400 mg once daily. If an additional dose reduction is required, sorafenib may be reduced to a single 400 mg dose every other day (see [Table 5-1](#)). A maximum of 2 dose reductions of sorafenib will be allowed per subject. Additional dose reductions not mentioned in [Table 5-1](#) will need to be discussed with the medical monitor.

Table 5-1 Sorafenib dose levels

Dose Levels	Sorafenib
0	400 mg twice daily
-1	400 mg once daily
-2	400 mg once every other day

Skin toxicity and hypertension are associated with sorafenib. Guidelines for the management of these events are provided in [Table 5-2](#) and [Table 5-3](#), respectively.

Skin Toxicity

Hand-foot skin reaction and rash are common in subjects treated with sorafenib. Management may include topical therapies for symptomatic relief, temporary treatment interruption and/or dose modification, or in severe or persistent cases, permanent discontinuation. Skin toxicities will be managed according to [Table 5-2](#).

Table 5-2 Dose modifications of sorafenib for skin toxicity

Skin Toxicity Grade	Occurrence	Suggested Dose Modification
Grade 1: Numbness, dysesthesia, paresthesia, tingling, painless swelling, erythema or discomfort of the hands or feet which does not disrupt the subject's normal activities.	Any occurrence	Continue treatment with sorafenib and consider topical therapy for symptomatic relief.
Grade 2: Painful erythema and swelling of the hands or feet and/or discomfort affecting the subject's normal activities.	1 st occurrence	Continue treatment with sorafenib and consider topical therapy for symptomatic relief. If no improvement within 7 days, see below.
	No improvement within 7 days or 2 nd or 3 rd occurrence	Interrupt sorafenib treatment until toxicity resolves to Grade 0-1. When resuming treatment, decrease sorafenib dose by 1 dose level (400 mg daily or 400 mg every other day).
Grade 3: Moist desquamation, ulceration, blistering or severe pain of the hands or feet, or severe discomfort that causes the subject to be unable to work or perform activities of daily living.	4 th occurrence	Discontinue sorafenib treatment.
	1 st or 2 nd occurrence	Interrupt sorafenib treatment until toxicity resolves to Grade 0-1. When resuming treatment, decrease sorafenib dose by 1 dose level (400 mg daily or 400 mg every other day).
	3 rd occurrence	Discontinue sorafenib treatment.

Hypertension

Hypertension is a known and potentially serious adverse event associated with sorafenib treatment. Subjects will have their blood pressure monitored and recorded. If the subject's blood pressure is elevated at any time ($> 150/100$ mmHg), even outside clinic visits, they will contact their study investigator. Guidelines for the management of hypertension are provided in [Table 5-3](#).

Table 5-3 Dose modifications of sorafenib for hypertension

Grade (CTCAE v3.0)	Antihypertensive Therapy	Blood Pressure Monitoring	Sorafenib Dose
Grade 1	None	Routine	No change
Grade 2 (asymptomatic)	Initiate monotherapy (suggest dihydropyridine calcium channel blocker)	Increase frequency and monitor by a health professional every 2 days until stabilized.	No change
Grade 2 (symptomatic/ persistent) OR diastolic BP > 110 mm Hg	Add agent(s): calcium channel blocker (if not already used), K ⁺ channel opener (angiotensin blockers), beta-blocker, thiazide diuretic	Increase frequency and monitor by health professional every 2 days until stabilized; continue monitoring every 2 days to stabilization after dosing restarted.	Hold* sorafenib until symptoms resolve and diastolic BP < 100 mm/Hg
Grade 3			Resume treatment at 1 dose level lower**
Grade 4	Discontinue sorafenib	Discontinue sorafenib	Discontinue sorafenib

*Subjects requiring a delay of > 21 days will discontinue sorafenib, unless in the study investigator's opinion, the subject may benefit from continued treatment.

AM01
21Dec10

**Subjects requiring > 2 dose reductions will discontinue sorafenib.

BP = Blood pressure.

Refer to NCI-CTCAE v4.0 for grade definitions.

(concluded)

Guidelines for the management of other non-hematologic and hematologic sorafenib-associated toxicities are provided in [Table 5-4](#). Those toxicities that are at least possibly related to an interaction with mapatumumab/placebo will have the mapatumumab toxicity guidelines in Section [5.1.4](#) applied.

Table 5-4 Dose modifications of sorafenib for sorafenib-associated toxicity

Toxicity	Grade 1	Grade 2	Grade 3*	Grade 4*
Non-hematologic	Continue at the same dose level	Continue at the same dose level	Withhold dose until toxicity is Grade ≤ 1, then resume treatment at the same dose level. If subject experiences a 2 nd Grade 3 toxicity, withhold dose until toxicity is Grade ≤ 1, then reduce dose to 400 mg orally daily and resume treatment.	Withhold dose until toxicity is Grade ≤ 1, then reduce dose to 400 mg daily and resume treatment, or discontinue at the discretion of the principal investigator after discussion with study sponsor.
Hematologic	Continue at the same dose level	Continue at the same dose level	Withhold dose until toxicity is Grade ≤ 2, then resume treatment at the same dose level. If subject experiences a 2 nd Grade 3 toxicity, withhold dose until toxicity is Grade ≤ 2, then reduce dose to 400 mg orally daily and resume treatment.	Withhold dose until toxicity is Grade ≤ 2, then reduce dose to 400 mg daily and resume treatment, or discontinue at the discretion of the principal investigator after discussion with study sponsor.

See [Table 5-2](#) and [Table 5-3](#) for dose modifications due to skin toxicity and hypertension respectively.

*Subjects who develop Grade 3 fever/chills, Grade 3 elevation of hepatic transaminases with ALT and AST < 10X upper limit of normal, Grade 3 hyperlipasemia or hyperamylasemia without clinical or other evidence of pancreatitis, Grade 3 leukopenia, or Grade 3/Grade 4 lymphopenia may continue sorafenib treatment without interruption at the discretion of the investigator.

Sorafenib Discontinuation

Temporary or permanent discontinuation of sorafenib will be considered in subjects who develop cardiac ischemia and/or infarction or severe or persistent hypertension despite institution of antihypertensive therapy. If a subject experiences a bleeding event that necessitates medical intervention or a gastrointestinal perforation, sorafenib will be permanently discontinued. Subjects, who undergo a surgical procedure or intervention to decrease portal hypertension, including transjugular intrahepatic portosystemic shunt, will discontinue sorafenib.

If the subject is withdrawn from further treatment with sorafenib, the subject may continue to receive mapatumumab/placebo alone every 21 days until radiologic progression or unacceptable toxicity.

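### Table 5-4 sets the reduced sorafenib dose at a fixed 400 mg daily, which is no reduction for a subject already at level -1

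*Protocol*

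**What the plan says.** The opening text of Protocol 5.2.3 gives two downward steps. First: "When a dose reduction is necessary, sorafenib dose may be reduced to 400 mg once daily". Second: "If an additional dose reduction is required, sorafenib may be reduced to a single 400 mg dose every other day". It also allows a reduction on wider grounds, "or if the investigator believes that a reduction in dose is warranted in the interest of subject safety", and sets a cap: "A maximum of 2 dose reductions of sorafenib will be allowed per subject". Reductions outside Table 5-1 go to the medical monitor.

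Table 5-1 lists the levels. Tables 5-2 (skin toxicity) and 5-3 (hypertension) express a reduction as one level down from wherever the subject is.

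Table 5-4 covers the remaining non-hematologic and hematologic toxicities, and the text introduces it as guidelines. Its four reduction cells name a dose instead of a step. In the two Grade 3 cells, a second Grade 3 toxicity leads to a hold until recovery, "then reduce dose to 400 mg orally daily and resume treatment". In the two Grade 4 cells the instruction is to hold, "then reduce dose to 400 mg daily and resume treatment", with an alternative: "or discontinue at the discretion of the principal investigator after discussion with study sponsor". The note under the table points to Tables 5-2 and 5-3 "for dose modifications due to skin toxicity and hypertension respectively". Neither the cells nor the notes say what to do for a subject who is already below full dose.

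**The concern.** A dose level belongs to the subject, not to the toxicity that caused it. A subject brought down to 400 mg daily for one reason carries that level into Table 5-4 when a different toxicity occurs. The table then says to reduce the dose and names the dose the subject is already taking.

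The state is foreseeable. Section 5.2.3 describes hand-foot skin reaction and rash as common under sorafenib, and Table 5-2 moves affected subjects down the ladder. Table 5-4 can also create the state by itself: a second Grade 3 toxicity takes a full-dose subject to 400 mg daily, and a later Grade 4 toxicity names 400 mg daily again.

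Patient safety and consistency between sites are at stake. Section 10.3 expects the protocol to be followed as written. One site could follow the table and restart a level -1 subject at the dose on which the toxicity occurred. Another could follow the text and restart at half that dose. Both could cite 5.2.3.

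**Working it through.** No stated figure needs reproducing. The check applies each rule to each starting level.

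Inputs from Table 5-1, as average daily dose:
- Level 0: 2 x 400 = 800 mg
- Level -1: 1 x 400 = 400 mg
- Level -2: 400 / 2 = 200 mg

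Target dose in the four reduction cells of Table 5-4: 400 mg per day.

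Change = (new dose - current dose) / current dose.

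| Current level | Table 5-4 as written | Ladder (5.2.3 text; the step used in Tables 5-2 and 5-3) |
|---|---|---|
| 0 | (400 - 800)/800 = -50% | (400 - 800)/800 = -50% |
| -1 | (400 - 400)/400 = 0% | (200 - 400)/400 = -50% |
| -2 | not addressed | no lower level; both permitted reductions used |

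At level 0 the two rules agree. At level -1 they differ, and the restart dose under the table is 400/200 = 2 times the ladder dose.

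Two routes lead to the level -1 problem:
1. Skin toxicity takes the subject from 800 to 400 mg/day under Table 5-2. A second Grade 3 toxicity of another kind, or a Grade 4 toxicity, then leads through Table 5-4 to 400 mg/day.
2. A second Grade 3 toxicity takes the subject from 800 to 400 mg/day under Table 5-4. A later Grade 4 toxicity leads through the same table to 400 mg/day, or to discontinuation.

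The grades differ in what they offer. The Grade 4 cells give a choice between 400 mg daily and stopping. The Grade 3 cells name neither a lower dose nor a stop, so there the site depends wholly on the general text.

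**The case against.** The case for leaving the table alone is substantial. Every subject starts at full dose, and from there 400 mg daily is exactly the first step in the text. The table is introduced as guidelines and sits inside 5.2.3, so it is naturally read together with the opening paragraph, whose second step is not limited to any toxicity. Tables 5-2 and 5-3 cover other, named toxicities, so a different rule there is not in itself a conflict. Nor is the missing pointer to Table 5-1 telling, since Tables 5-2 and 5-3 do not cite it either. A footnote to Table 5-4 lets several Grade 3 events, and Grade 3 or 4 lymphopenia, continue without interruption at the investigator's discretion. Harm requires a subject at level -1, a further qualifying toxicity, and an investigator who puts the table above the text.

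Most of this stands, and it confines the point to already-reduced subjects. It does not remove the point. At level -1 a site can reduce the dose or give 400 mg daily, but not both, and the cell asks for both.

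A reader might infer three stronger things that the documents do not support:
- *That the table raises a level -2 subject from 200 to 400 mg/day.* The cell says to reduce. Such a subject has also used both permitted reductions, and anything further goes to the medical monitor.
- *That the table allows only one of the two reductions.* The table does not operate alone. It does not bar level -2, and the general text supplies that step.
- *That subjects are left with no lower dose and no way to stop.* The text permits every-other-day dosing, and the Synopsis and Section 6.6 allow treatment to end for unacceptable toxicity.

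**Conclusion.** The point holds for subjects already at level -1. Read literally, Table 5-4 restarts them at an unchanged 400 mg daily after a second Grade 3 or a Grade 4 toxicity, twice the dose the ladder would give. It does not hold as a general conflict between Table 5-4 and the ladder, because the two agree at full dose and the text of 5.2.3 remains available at level -1.

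The conclusion rests on a literal reading of the four cells and on average daily dose as the measure. The documents give no rate of earlier dose reductions, so the number of subjects affected cannot be estimated.

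The consequence is a modest safety and consistency issue. The rule is the same in both arms and has no bearing on the endpoint, the sample size, the power or the primary analysis. At most, the descriptive sorafenib exposure summaries in SAP 6.2 would depend slightly on which reading a site followed. It should be corrected because the remedy is so small, not because the expected harm is large.

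**What to change.** In all four reduction cells of Table 5-4, replace the fixed 400 mg dose with *by 1 dose level (Table 5-1)*. Add one note under the table: *Subjects already at level -2 have used the maximum of 2 dose reductions and should stop sorafenib unless a further reduction is agreed with the medical monitor (Section 5.2.3).*

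A full-dose subject still goes to 400 mg daily. A level -1 subject goes to 400 mg every other day. The Grade 4 discontinuation option and the medical-monitor route stay as they are, and Tables 5-2 and 5-3 need no change.

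The cost is one phrase in four cells and one note, with no change to any endpoint, sample size or analysis. The same fixed dose stands in the original protocol and in Amendments 1, 2 and 3, so the correction would have done most good at the start. Appendix 9 records that at least 90% of subjects had met the survival endpoint by Amendment 3. If enrolment was near the planned 100 or so, at most about 100 x (1 - 0.90) = 10 subjects were still alive, and only those still on sorafenib, including under extended access (Section 6.4), could benefit.

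### Table 5-4 sets a fixed sorafenib dose of 400 mg daily where Tables 5-2 and 5-3 step down one level, so for a subject already reduced its literal instruction is no reduction

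*Protocol*

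**What the plan says.** All the rules are in Protocol Section 5.2.3. Table 5-1 defines three sorafenib dose levels: level 0 is 400 mg twice daily, level -1 is 400 mg once daily, and level -2 is 400 mg every other day.

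The general text sets out a two-step ladder. The first step is "When a dose reduction is necessary, sorafenib dose may be reduced to 400 mg once daily". The second is "If an additional dose reduction is required, sorafenib may be reduced to a single 400 mg dose every other day". The cap is "A maximum of 2 dose reductions of sorafenib will be allowed per subject", and reductions outside Table 5-1 "will need to be discussed with the medical monitor". The same paragraph lets the investigator reduce the dose on safety grounds.

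Tables 5-2 (skin toxicity) and 5-3 (hypertension) express a reduction relative to the current dose: the subject resumes one level lower. Table 5-2 names both possible landing doses in brackets. A footnote to Table 5-3 has subjects who need more than two reductions stop sorafenib.

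Table 5-4 covers the remaining toxicities, in a non-hematologic and a hematologic row. After a first Grade 3 event the site withholds sorafenib until recovery, "then resume treatment at the same dose level". After a second, it withholds, "then reduce dose to 400 mg orally daily and resume treatment". After a Grade 4 event it withholds, "then reduce dose to 400 mg daily and resume treatment, or discontinue at the discretion of the principal investigator", following discussion with the sponsor. A footnote lets certain Grade 3 events, and Grade 3 or 4 lymphopenia, continue without interruption. The table points to Tables 5-2 and 5-3 for their own toxicities, but not to Table 5-1 or level -2.

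**The concern.** Table 5-4 is meant to escalate: the first Grade 3 event leaves the dose unchanged and the second lowers it. A fixed target does this only for a subject still on the full dose. At level -1 the second-event instruction gives the same dose as the first-event instruction.

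The case is foreseeable. Level -1 is the first step of every reduction, and Section 5.2.3 says "Hand-foot skin reaction and rash are common in subjects treated with sorafenib". A subject reduced for skin toxicity who later has a second Grade 3 event of another kind is in exactly this position. A site that follows the cell resumes the dose the subject was on when the toxicity recurred; a site that follows the paragraph above the tables may halve it. What is at stake is subject safety and consistent management of toxicity.

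**Working it through.** The protocol states no figure to reproduce here. The check applies each table's wording to each dose level and compares average daily doses.

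**Average daily dose (Table 5-1)**
- Level 0: 2 × 400 = 800 mg/day
- Level -1: 1 × 400 = 400 mg/day
- Level -2: 400 / 2 = 200 mg/day

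**Dose on resuming**, with change = (new − current) / current

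| Current level | Reductions used, of 2 | One level down (Tables 5-2, 5-3) | Table 5-4 read literally |
|---|---|---|---|
| 0 (800 mg/day) | 0 | 400; (400 − 800)/800 = −50% | 400; −50% |
| -1 (400 mg/day) | 1 | 200; (200 − 400)/400 = −50% | 400; (400 − 400)/400 = 0% |
| -2 (200 mg/day) | 2 | no lower level; cap reached | 400; (400 − 200)/200 = +100% |

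The rules agree at level 0 and part at levels -1 and -2. At level -1 the literal reading also leaves the second permitted reduction unused.

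**Cells involved.** Two rows (non-hematologic, hematologic) × two columns (Grade 3, Grade 4) = 4 cells. The 2 second-Grade-3 instructions offer no alternative within the cell. The 2 Grade 4 cells also allow discontinuation, so the problem arises there only if treatment is resumed. These are counts of table entries, not of subjects.

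**Routes to level -1.** Tables 5-2 and 5-3 are the clear ones. Table 5-4 is a narrow one. A subject who reached 400 mg daily because of a second Grade 3 event would next have a third, which the cell does not address. What remains is an earlier Grade 4 event, or counting Grade 3 events separately in the two rows. The footnoted exemptions narrow the case further.

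**Check against the SAP.** SAP Section 6.2 (Extent of Exposure) defines a sorafenib dose reduction relative to the previously prescribed dose. On that definition 400 to 400 mg/day is not a reduction.

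**The case against.** The strongest reply is that Section 5.2.3 already supplies the answer. Its general text gives the second step to 400 mg every other day, allows reduction on safety grounds and caps reductions at two. Table 5-4 is introduced as guidance. Its cell says to reduce, which cannot be done by resuming an unchanged dose, so a sensible reader goes back to the ladder. Section 6.6 also allows withdrawal when unacceptable toxicity continues.

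Most of this stands. A reader might infer from Table 5-4 that a subject at level -1 is barred from a lower dose, or that a subject at level -2 must go back up. The documents do not support either: the ladder and the safety clause permit the lower dose, the cap governs level -2, and the verb in the cell shows that a lower dose was intended. Nor do the documents show that sites did diverge.

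What the reply does not remove is the inconsistency. The general text permits the second step without requiring it, and it sends sites to the tables for the detail. The table for these toxicities names a single dose and has no pointer to Table 5-1. A dosing instruction in a safety rule should not have to be set aside by inference.

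It is also fair to say that an amendment now would help few subjects. Appendix 9 records that at least 90% have met the survival endpoint. If about 100 were enrolled as planned, at most about 10 remain (10% × 100), and not all of those need be on sorafenib.

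**Conclusion.** The point holds as a limited internal inconsistency in a safety rule. Read literally, Table 5-4 gives a 0% change at level -1, where its sibling tables give −50%, and a rise from 200 to 400 mg/day at level -2. It matches them only at level 0. The conclusion rests on reading the cells as written and on average daily doses from Table 5-1. The number of subjects affected is unknown; the documents give no basis for estimating it.

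A reader might also infer that the trial's results are affected. Nothing in the documents supports that: the inconsistency does not alter the definition or analysis of time to progression, the sample size or any SAP rule. The correction is worth making on safety grounds, but it is not a reason to question the design.

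**What to change.** In the Grade 3 (second event) and Grade 4 cells of both rows of Table 5-4, replace the fixed 400 mg daily with *reduce by 1 dose level (Table 5-1)*. Keep the Grade 4 option to discontinue. For subjects already at level -2, state that sorafenib is discontinued, as the Table 5-3 footnote does, subject to the medical monitor discussion in the general text of Section 5.2.3. That discussion comes from the text; Table 5-3 contains no such exception.

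The cost is a wording amendment to four cells and one cross-reference, with the investigator signature and IRB/IEC submission that Section 10.4 requires for any amendment. There are no added procedures and no SAP change. Some subjects at level -1 would receive 400 mg every other day instead of 400 mg daily, a step Section 5.2.3 already permits. If no amendment is otherwise planned, the wording can go into the next one.
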